Official title: The Antibacterial Effect of Nanosilver Fluoride in Relation to Caries Activity in Primary Teeth: a Randomized Controlled Clinical Trial

NCT number: NCT05221749

Date uploaded: 25th July, 2023

**THE ANTIBACTERIAL EFFECT OF NANOSILVER
FLUORIDE IN RELATION TO CARIES ACTIVITY IN
PRIMARY TEETH:
A RANDOMIZED CONTROLLED CLINICAL TRIAL**

2021/2022

ABSTRACT

Background: Dental caries is among the most prevalent chronic diseases in children. Minimally invasive dentistry is a highly convenient and efficient method of managing caries in pediatric patients. Recently, Nanosilver fluoride (NSF) has emerged as a promising topical fluoride agent with a potent cariostatic and antibacterial potential. This new anticaries agent is used as an alternative to overcome the drawbacks of topical fluoride and silver diamine fluoride (SDF) in caries prevention.

Objective: To assess the antibacterial effect of NSF in relation to caries activity in dentin caries lesions of primary teeth in comparison to SDF after 1 month.

Methods: Fifty children aged 4 to 6 years old with active dentin caries lesions according to ICDAS score 5 will be recruited from the Pediatric Dentistry clinic at the Faculty of Dentistry, Alexandria University. The children will be equally and randomly allocated into 2 groups; the first group will be treated using NSF, while the second group will be the control group receiving SDF treatment. Microbiological assessment using a microbrush will be done at baseline and follow-up appointments to record the bacterial counts using the suitable culture media, the results will be expressed in colony forming units (CFU). Data regarding the children's oral health will be collected and their dmf index will be scored. The arrest of active carious lesions will be measured after 1 month according to ICDAS criteria and a microbiological assessment will be completed.

Results: The relation between bacterial counts (CFU) and lesion activity for both interventions will be assessed. The data collected will be statistically evaluated with the suitable tests and tabulated.

Keywords: Nanosilver fluoride, silver diamine fluoride, antibacterial, caries arrest, microbiology, primary teeth, pediatric, clinical trial

INTRODUCTION

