*** Himedia Laboratories, Mumbai, India.

****Red line by binder

Method

First visit: baseline examination

After obtaining the informed consent from the care giver/parent, the researcher will provide oral hygiene instructions to each of the study participants and will inform them about the importance of maintaining good oral hygiene and a proper diet.²⁹ The patients and caregivers will be informed about the therapeutic intervention to be applied, the possible outcomes, and side effects in detail. All of the examinations and interventions will be done by one calibrated examiner. All of the lesions in the children's oral cavity indicated for treatment with NSF or SDF will be treated and sampled for microbiological analysis.³⁰

On the day of the intervention, the children will be asked to refrain from tooth brushing in the morning, as well as eating and drinking (except water) for at least two hours before the appointment. The dmf index will be recorded for each patient.

For caries treatment in all groups, no caries or unsupported enamel will be removed. The patients will be instructed to rinse with a cup of water, then any gross debris will be gently removed with a piece of gauze. The tooth will then be partially isolated using cotton rolls and a saliva ejector. Additionally, petroleum jelly will be applied to the gingiva for added protection. Before applying the intervention, a 2-mm wide microbrush will be rubbed on the carious lesion for 4 seconds to collect the baseline microbiological sample.⁶ The microbrush will then be inserted in a sterile test tube containing 1 mL of saline and transported to the microbiology laboratory within 1-2 hours.³¹

Intervention

Test group (NSF):

- 1 drop of NSF will be dispensed into a sterile plastic dappen dish.

- Affected tooth surfaces will be dried with a gentle flow of air.
- The solution will be applied to the carious lesions using a microbrush.
- No more than one drop of NSF will be used for each patient.
- The NSF solution will be left in contact with the tooth surface for 1 minute.³²
- Any excess will be removed with a cotton pellet to minimize systemic absorption.

Control group (SDF):

It will be applied according to the manufacturer's instructions and the AAPD guidelines for using SDF.^{28,30}

- One drop of 38% SDF will be dispensed into a sterile plastic dappen dish.
- Affected tooth surfaces will be dried with a gentle flow of air.

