All patients will be recalled after one month. On the day of the recall appointment, patient preparation will be done as mentioned before.

Outcome assessment

- Microbiological assessment will be done as mentioned before and CFU counts will be recorded.
- Lesion activity will be assessed according to the ICDAS criteria. Using a blunt ended probe, if the cavity is found to be shiny and feels hard on gentle probing of the dentin, it will be recorded as an inactive lesion. While if it remains soft or leathery on gentle probing, it will be recorded as an active lesion.

STUDY PLAN

[figure not shown]

Figure: flow chart of the study plan

STATISTICAL ANALYSIS

The statistical software SPSS version 27.0 for Windows will be used for data analysis. The outcome variable is the number of colony forming units (CFU) of *streptococcus mutans and lactobacilli*, and the number of arrested caries lesions after 1 month in both the SDF and NSF groups. The collected data will be recorded and statistically evaluated.

The Chi square test will be used to compare the difference between the two groups regarding change caries lesion activity, the T-test or the Mann-Whitney U test will be used to analyze the differences between the microbiological samples, Wilcoxon signed rank will be used to assess the changes over time in bacterial counts. Regression analysis will be used to assess the potential confounders such as gender, social status, and dietary habits. The data will be graphically presented with suitable graphs. The level of statistical significance will be set at 5%.

ETHICAL CONSIDERATIONS IN SUBJECTS INVOLVING HUMAN SUBJECTS

1. This research protocol will be approved by the Research Ethics Committee of Alexandria University Faculty of Dentistry (IORG 0008839-IRB No. 0359-12/2021). prior to any research-related activities.
2. All research activities involving human subjects will abide by the Declaration of Helsinki³⁷ and other ethical guidelines adopted by the Research Ethics Committee of Alexandria University Faculty of Dentistry.
3. Benefits:
 - It will provide a caries arresting treatment for young children with multiple active carious lesions using minimally invasive atraumatic procedures.
 - It will allow overcoming the disadvantages of silver diamine fluoride including black staining of the teeth and any clothes it contacts, soft tissue injury, unpleasant taste for children.

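### The unit of analysis is not stated: children are randomised, every indicated lesion is sampled, and no planned test allows for clustering within a child

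*Combined protocol and SAP*

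**What the plan says.** The Grouping section allocates participants, that is children, to the two arms. Sample size estimation asks for 24 children per group, raised to 25. The Inclusion Criteria require one qualifying lesion as a minimum and set no maximum.

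Under Method, first visit, all lesions in the mouth "indicated for treatment with NSF or SDF will be treated and sampled for microbiological analysis". The Benefits item under Ethical Considerations describes the recipients as "young children with multiple active carious lesions using minimally invasive atraumatic procedures".

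The Statistical Analysis section lists bacterial counts as an outcome, together with "the number of arrested caries lesions after 1 month in both the SDF and NSF groups". The tests are:

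- Caries activity: "The Chi square test will be used to compare the difference between the two groups regarding change caries lesion activity".
- Bacterial counts between groups: "the T-test or the Mann-Whitney U test will be used to analyze the differences between the microbiological samples".
- Bacterial counts within groups: "Wilcoxon signed rank will be used to assess the changes over time in bacterial counts".
- Covariates: "Regression analysis will be used to assess the potential confounders such as gender, social status, and dietary habits".

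The Abstract adds a further analysis: "The relation between bacterial counts (CFU) and lesion activity for both interventions will be assessed". No test is named for it.

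The readable text gives no index lesion, no rule for reducing several lesions to one value per child, and no random effect, GEE or cluster-robust standard error. The study flow chart is not shown in the copy reviewed.

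**The concern.** Lesions in one mouth share saliva, diet, hygiene and a treatment session, so their outcomes are likely to be positively correlated. Every test named in the plan assumes independent observations (independent pairs, for the Wilcoxon test). Entering each lesion or sample as a separate observation overstates the information in the data, and the standard errors come out too small.

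The 5% significance level is then not met. A chance difference between NSF and SDF, or a chance change in counts over the month, would be called significant too often. The gap touches every inferential comparison: both organisms, arrest, change over time, the confounder regression, and the relation between counts and activity. As written, a reader cannot tell whether a reported p-value would be valid.

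**Working it through.** **Inputs from the documents.** Significance level 5% (Statistical Analysis; two-sided assumed); 24 children per arm (Sample size estimation); the child as the randomised unit (Grouping); one or more lesions per child (Inclusion Criteria).

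**Assumed inputs, not in the documents.** Lesions per child (m), ICC, arrest rate, and correlations between visits.

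**The plan's own figure.** The 24 per group cannot be reproduced, because no effect size or standard deviation is given. Solving backwards at 80% power, two-sided 5%, the normal approximation gives a standardised difference of (1.96 + 0.84) × √(2/24) = 0.81; the t-test calculation gives 0.83. Either way, the unit of that calculation is the child.

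**Step 1. Type I error of a lesion-level test.** With m lesions in every child, the design effect is DE = 1 + (m − 1) × ICC. With unequal counts it is DE = 1 + (E[m²]/E[m] − 1) × ICC. The actual two-sided error is 2 × (1 − Φ(1.96/√DE)).

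Example: m = 3, ICC 0.3. DE = 1 + 2 × 0.3 = 1.6; 1.96/√1.6 = 1.55; error 12.1%. The 3 × 24 = 72 lesions per arm carry the information of 72/1.6 = 45.

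Mixed counts (half the children with 1 lesion, a quarter with 2, a quarter with 3): E[m] = 1.75, E[m²] = 3.75, ratio 2.14.

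| Lesions per child | DE, ICC 0.1 | Error | DE, ICC 0.3 | Error |
|---|---|---|---|---|
| 1 | 1.0 | 5.0% | 1.0 | 5.0% |
| Mixed 1 to 3 | 1.11 | 6.3% | 1.34 | 9.1% |
| 2 | 1.1 | 6.2% | 1.3 | 8.6% |
| 3 | 1.2 | 7.4% | 1.6 | 12.1% |
| 4 | 1.3 | 8.6% | 1.9 | 15.5% |

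**Step 2. Simulation with no true effect, 24 children per arm.**

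- Arrest, lesion-level chi-square (beta-binomial, arrest rate 50%, 70% or 85% in both arms). At ICC 0.1 and 0.3 the error was 6.1–7.0% and 8.7–9.7% with 2 lesions, 7.2–8.2% and 12.1–13.0% with 3 lesions, and 6.2–6.8% and 8.8–9.2% with mixed counts. With one lesion per child the chi-square already runs at 5.2–6.0%; that part is discreteness, not clustering.
- Change in bacterial counts, lesion-level t-test / Mann-Whitney / Wilcoxon. With 2 lesions the error was 6.3 / 6.5 / 6.4% (ICC 0.1) and 8.6 / 8.2 / 8.0% (ICC 0.3). With 3 lesions it was 7.2 / 7.0 / 7.0% and 12.4 / 11.7 / 12.3%.

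**Step 3. The ICC of a change may be lower than that of arrest.** Stable child factors partly cancel. Let c be the ICC at each visit, ρ the between-visit correlation of child effects, and τ that of lesion effects. Then ICC of change = c(1 − ρ) / [c(1 − ρ) + (1 − c)(1 − τ)]. With c = 0.3 and ρ = 0.7, this is 0.09/0.79 = 0.114 at τ = 0 and 0.09/0.58 = 0.155 at τ = 0.3. The error is then 6.3–6.8% with 2 lesions and 7.7–8.7% with 3.

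**Step 4. Counts against activity, lesion by lesion.** With the same ICC for both variables, DE = 1 + (m − 1) × ICC². For 2 to 3 lesions and ICC 0.1 to 0.3 the error is 5.1–7.1%; simulation with 48 children gave 5.0–7.5%.

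**Step 5. Do the remedies restore the level?** Simulated error was 4.4–5.3% for tests on per-child means of count change, and 4.2–5.4% for Mann-Whitney on per-child arrest proportions. GEE for arrest with a plain robust z-test gave 6.1–6.7%. With an n/(n − 1) correction and a t reference on 46 degrees of freedom it gave 4.8–5.6%.

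**The case against.** The strongest reply is that the plan never says lesions will be treated as independent observations, and that parts of it point to the child. The PICOT question, the sampling instruction and the activity assessment speak of one lesion or cavity. The named confounders are child attributes. The sample size and drop-out allowance are in participants. The statement about multiple lesions is a general benefit claim, not an enrolment forecast. Lesions per child and ICC are assumed, and the 12% figure needs 3 lesions per child with an ICC of 0.3. For the change in counts, which is the outcome in the PICOT question, the worked example gives only 6.3–8.7%.

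Much of this stands as a limit on certainty. The inflation is conditional, its size is not known, and a lesion-level analysis is not proven to be intended.

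It does not remove the problem. The first-visit section has all indicated lesions sampled, and the singular in the sampling instruction fits a procedure repeated for each lesion. If one lesion per child is meant, nothing says which, and a choice made after the data are seen is a flaw of its own. For arrest, the outcome is a count of lesions tested by chi-square, so following the text most naturally gives a lesion-level test. Child-level covariates do not settle the unit, since they can enter a lesion-level regression too.

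**Conclusion.** The concern holds, and the plan must be changed. The design yields several correlated observations per child, and the analysis section neither states the unit nor allows for the correlation. If lesions are entered directly, the type I error exceeds the nominal 5% whenever children contribute more than one lesion and lesions within a child are positively correlated.

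The size rests on assumptions: about 6% to 12% for 2 to 3 lesions per child at ICC 0.1 to 0.3, and more with more lesions or a higher ICC. Bacterial-count change may sit in the lower part of that range, and the relation between counts and activity is affected least. Confidence is high in the omission and in the direction of the error, not in any single figure. With one value per child, or a model clustered on child, the problem does not arise.

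**What to change.** State in the Statistical Analysis section that inference respects the child as the randomised unit. For between-group and over-time comparisons, choose one option in advance:

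- **(a) One value per child.** Apply the planned t-test or Mann-Whitney, and the Wilcoxon, to each child's mean change in log CFU over the sampled lesions, separately for each organism and with a stated rule for zero counts. Compare per-child proportions of arrested lesions by Mann-Whitney in place of chi-square.
- **(b) A lesion-level mixed model or GEE** with child as the cluster and a small-sample correction, since there are only about 24 children per arm.

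A single index lesion per child, selected by a rule fixed beforehand, would also be valid and would keep the listed tests, but it leaves the other sampled lesions unused.

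For the relation between counts and activity, keep each lesion's count paired with its own activity and use a mixed model or GEE clustered on child. Treat the confounder regression in the same way. Report the number of treated lesions per child by group.

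The cost is a few sentences, using data already to be collected; no extra children, visits or samples. The 24 per group keeps its stated unit under (a). The downsides are these: p-values will usually be larger, and correct, when children have several lesions. Under (a) the arrest comparison weights children equally rather than lesions, and child averages cannot serve the count-activity relation, so that analysis needs the clustered lesion-level model in any case. Option (b) depends on the small-sample correction being applied.

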Interestingly, it is unknown if the reduction in caries activity brought about the use of nanosilver fluoride is due to its remineralizing action, antibacterial action, or due to a combination of both.^{17,18} There is a need to understand the interaction of topical caries arresting agents like NSF and SDF with the oral microbiome associated with dental caries, since the in vitro findings cannot be extrapolated to the clinical use of NSF.¹⁹

To our knowledge, no publication has reported the in vivo antimicrobial efficiency of NSF on the primary dentition in comparison to SDF. Therefore, this study will be undertaken to evaluate and compare the clinical antibacterial and cariostatic effectiveness of NSF compared to that of SDF in 4-6 year old children. The null hypothesis of this study is that no statistically significant difference will be detected regarding the antibacterial effect of nanosilver fluoride in relation to caries activity in dentin caries lesions of primary teeth, in comparison to silver diamine fluoride, after one month.

AIM OF THE STUDY

General aim

To assess the antibacterial effect of nanosilver fluoride in relation to caries activity in dentin caries lesions of primary teeth in comparison to silver diamine fluoride after one month.

Specific aims

- To compare the change in *Streptococcus mutans* and *Lactobacilli* counts in dentin caries lesions of primary teeth after one month of the application of nanosilver fluoride or silver diamine fluoride.
- To compare the effect of nanosilver fluoride to that of silver diamine fluoride on caries lesion activity in dentin caries lesions of primary teeth after one month of application according to ICDAS criteria.

MATERIALS AND METHODS

Study Design

This will be a randomized, parallel, two-arm clinical trial, with a 1:1 allocation ratio. It will be set up and reported according to the CONSORT guidelines.²⁰

The PICOT question is: will children (4-6 years old) with an active carious lesion (ICDAS code 5) (population; P) using nanosilver fluoride varnish (Intervention; I) in comparison to silver diamine fluoride (comparison; C) show a greater percentage decrease in bacterial counts in the caries lesion (outcome; O) after 1 month follow-up (time; T)?

Study Setting and Location

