- A microbrush will be dipped into the SDF and dabbed on the side of the dappen dish to remove excess liquid before applying the solution to only the affected tooth surface.
- No more than one drop of SDF will be used for each patient.
- The SDF will be allowed to dry on the lesion for 1 minute.³³
- Any excess will be removed with a cotton pellet to minimize systemic absorption.

After the application of fluoride agents, all of the children will be instructed not to drink or eat for 1 hour after the appointment, their parents will be asked to observe this instruction.²⁴ Additionally, for ethical considerations, teeth not treated with SDF or NSF or those showing signs of failure or any new carious lesions that will appear during follow-up period will be appropriately treated.

Microbiological Procedure

1. Sample dilution

All samples will be dispersed by vortexing for 30 seconds then 10-fold serially diluted using sterile saline. A measure of the dilution will then be used for traditional plate culturing methods.^{34,35}

2. Culture

Aliquots of 10 ml of each dilution will be inoculated into freshly prepared Mitis Salivarius agar and Rogosa agar media respectively, using a micropipette.

- Mitis Salivarius agar plates will be incubated anaerobically in an atmosphere containing 10% CO₂ at 37°C for 72 hours to detect *Streptococcus mutans* counts.
- Rogosa agar plates will be incubated aerobically at 37° C for 48 hours to detect *Lactobacilli* count.

3. Isolation and Enumeration

Following the predetermined incubation period, colonies grown on the specified media will be counted and represented as (CFU/ml). *Streptococcus mutans* will be identified based on their characteristic morphology on Mitis Salivarius agar plates. Similarly, *Lactobacilli* will be identified biochemically and microscopically on the basis of their morphology.

4. Colony count

The number of colonies will be determined and expressed as colony forming units using the following equation.³⁶

$$\text{CFU/ml} = \frac{\text{n}^{\circ} \text{ of colonies} \times \text{dilution factor}}{\text{Volume taken in ml (1)}}$$

STUDY OUTCOME

Treatment effect will be evaluated after one month by comparing:

- Microbiological assessment of colony forming units (CFU) of *Streptococcus mutans* and *Lactobacilli*.
- Caries activity according to ICDAS criteria.

Follow up

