Appendix I

Table (1): ICDAS severity criteria³⁸

Score	Criteria
0	No change in enamel translucency with prolonged air drying
1	First visual change in enamel (after prolonged air drying)
2	Distinct visual change in enamel
3	Localized enamel breakdown or discolored enamel with no visible dentine involvement
4	Underlying dark shadow from dentine
5	Distinct cavity with visible dentine
6	Extensive distinct cavity with visible dentine

Table (2): ICDAS caries activity criteria³⁸

ICDAS code	Characteristics of Lesion	
	Active Lesion	Inactive Lesion
1, 2 or 3	Surface of enamel is whitish/yellowish opaque with loss of luster; feels rough when the tip of the probe is moved. Lesion is in a plaque stagnation area, i.e.: pits and fissures, near the gingival and approximal surface below the contact point.	Surface of enamel is whitish, brownish or black. Enamel may be shiny and feels hard and smooth when the tip of the probe is moved. For smooth surfaces, caries lesion is typically located at some distance from the gingival margin
4	Probably active	
5 or 6	Cavity feels soft or leathery on gently probing the dentin	Cavity may be shiny and feels hard on gently probing the dentin.

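### Does the one-month activity rule leave a hard cavity that is not shiny without a category?

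*Combined protocol and SAP*

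**What the plan says.** The Outcome assessment section sets the standard first: "Lesion activity will be assessed according to the ICDAS criteria". It then gives the probing rule. A lesion is inactive "if the cavity is found to be shiny and feels hard on gentle probing of the dentin". The other limb reads: "While if it remains soft or leathery on gentle probing, it will be recorded as an active lesion". There is no third category and no default.

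Appendix I, Table (2), covers codes 5 and 6 in one row. Active: "Cavity feels soft or leathery on gently probing the dentin". Inactive: "Cavity may be shiny and feels hard on gently probing the dentin".

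The same standard is named elsewhere. The Abstract says: "The arrest of active carious lesions will be measured after 1 month according to ICDAS criteria". The second specific aim compares the treatments "on caries lesion activity in dentin caries lesions of primary teeth after one month of application according to ICDAS criteria". Study Outcome lists "Caries activity according to ICDAS criteria". The inclusion criteria refer to ICDAS severity and activity and point to Appendix I, Tables 1 and 2.

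Statistical Analysis names the number of arrested lesions at one month as an outcome variable and compares lesion activity between arms by chi-square. The baseline visit section assigns all examinations to one calibrated examiner, and Blinding says the investigator knows the treatment.

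**The concern.** The operative sentence joins shine and hardness with a plain conjunction. In the table the permissive verb attaches to shine alone, while hardness is stated flatly. The sentence looks like a paraphrase of the table that lost this qualifier, and the loss changes its literal meaning.

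Arrest is a binary outcome in 50 children, so its two categories should cover every lesion. If one type of lesion has no category, the examiner must settle it by judgement while knowing the treatment, or leave it blank. Blanks would shrink the chi-square denominators and cost some power. No sentence states expressly that the appendix prevails over the body text at follow-up.

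**Working it through.** **Step 1. Cross shine with texture and apply both texts.** The plan gives no figure to reproduce here; the check is one of wording.

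| Cavity | Outcome assessment | Appendix I, Table (2) |
|---|---|---|
| Shiny, hard | inactive | inactive |
| Shiny, soft or leathery | active | active |
| Not shiny, soft or leathery | active | active |
| Not shiny, hard | not named | inactive |

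Three cells agree. In the fourth the texts do not give opposite answers: one is silent and the other says inactive.

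**Step 2. Fill the silent cell from the plan.** The rule's opening sentence adopts ICDAS, and the document holds one ICDAS activity table. Both texts make softness the mark of activity, so a hard cavity cannot be active under either. With two categories and one ruled out, inactive is what remains, and the table says so directly. Entry is unaffected, because it requires an active lesion and the texts agree on what active means.

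**Step 3. Size of the harm if hard cavities without shine were left uncoded.** All inputs except the 25 children per arm are assumptions: one lesion per child (a simplification, since the plan treats every indicated lesion), share truly hard h = 0.80 v 0.50, and share f of hard lesions without shine equal in both arms.

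- Expected uncoded lesions per arm = 25 × h × f. At f = 0.10: 25 × 0.80 × 0.10 = 2.0 and 25 × 0.50 × 0.10 = 1.25. At f = 0.30: 6.0 and 3.75.
- Recorded inactive share = h(1 − f) / (1 − hf). At f = 0.10: 0.72 / 0.92 = 0.783 and 0.45 / 0.95 = 0.474, a difference of 0.309. At f = 0.30: 0.56 / 0.76 = 0.737 and 0.35 / 0.85 = 0.412, a difference of 0.325.
- Power is for the Pearson chi-square without continuity correction, two-sided 5%. The exact figures enumerate all outcomes and average over the binomial number of coded lesions. The smooth figures are a normal approximation at the expected numbers coded.

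| f | Recorded difference | Exact power | Smooth power |
|---|---|---|---|
| 0 (Table 2 reading) | 0.300 | 63.8% | 60.9% |
| 0.10 | 0.309 | 60.7% | 59.3% |
| 0.20 | 0.317 | 58.6% | 57.3% |
| 0.30 | 0.325 | 56.4% | 55.0% |

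Here the recorded difference does not shrink, and the exact power loss is about 3 to 7 points. Adding the pairs 90% v 60%, 70% v 40% and 60% v 30%, the recorded difference runs from 28.1 to 35.1 points, the smooth loss from 1 to 9 points and the exact loss from 2 to 13. The top of the exact range is partly a step effect of the test. For 70% v 40%, exact power with 24, 25, 26 and 27 per arm is 0.590, 0.622, 0.583 and 0.586, so 25 is a local peak and losses measured from it are overstated.

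With equal h and equal f in both arms, the recorded shares are also equal, so this mechanism creates no difference under the null.

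**The case for a change.** The strongest case for acting is that the Outcome assessment sentence says what goes on the form, and a specific instruction is usually read ahead of a general reference to a standard. The pointer to Appendix I sits under eligibility and is not a precedence clause for follow-up. The examiner is unblinded, and SDF is expected to blacken lesions, so the share without shine need not be equal across arms as assumed above. Aligning the sentence with the table would cost almost nothing.

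Part of this stands. The texts differ in one cell, and no sentence ranks them. What does not follow is a consequence. Nothing in the plan allows a lesion to be left unrecorded, and nothing supports calling a hard one active, so whether shine differs by arm does not matter once hardness decides. Knowledge of treatment when judging hardness is a separate matter, which the wording on shine neither causes nor cures. The content of the examiner's calibration is not described, so it offers only modest reassurance.

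**Conclusion.** This is an editorial slip, a qualifier lost in paraphrase, and no change to the plan follows. The plan's own references to ICDAS lead to Table (2), under which a hard cavity is inactive whether or not it shines. On that reading the arrest count, the chi-square comparison and the error rate are unchanged.

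The conclusion rests on the examiner classifying by hardness, as the named standard and the texture-only definition of active both direct. The power losses shown apply only if hard cavities were left blank, and they rest on assumed rates; the documents give no arrest rate, no frequency of shine and no number of lesions per child. They limit a hypothetical and should not be cited as an effect on this trial.
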